Study Visit day 0: Subjects will come fasting for this visit. Each subject will be given one injection of Liraglutide 1.2 mg or placebo. A fructosamine and blood samples will be collected at baseline. Blood samples will be collected after the baseline at 30, 60, 120, 180, 240 and 300 minutes after the injection. (**This is being done to evaluate the acute effect of a single injection of Liraglutide on oxidative stress and inflammatory mediators, before any adjustments of insulin dose or effect of Liraglutide on blood glucose and weight is evident**). Subjects will be instructed by the study staff in the dosing and administration of the study medication. They will start Liraglutide injection at a dose of 0.6 mg per day or placebo injection on the following day. We will adjust the doses of basal and bolus insulin to eliminate low blood sugars(less than 70 mg/dl). At all subsequent visits insulin doses will be titrated to target blood sugars between 70-180 mg/dl at all times. Patients will return to the center after 7 days.

Study Visit week 1: Blood glucose concentrations will be reviewed. Insulin dose will be adjusted at the discretion of the study investigator to optimize blood sugar control as per

the targets mentioned above. Patients will be advised to increase the Liraglutide dose to 1.2 mg a day if they are able to tolerate the 0.6 mg dose. If they are experiencing mild nausea, subjects will continue with 0.6 mg daily for another 7 days. Those with severe nausea/vomiting will be dropped from the study. All other subjects will return in 7 days.

Study Visit week 2: Blood glucose concentrations will be reviewed. Insulin dose will be adjusted if needed. Subjects taking 0.6 mg dose and experiencing significant nausea will be dropped from the study. Subjects on 1.2 mg and experiencing significant nausea will decrease the dose to 0.6 mg and continue that dose for the duration of the study. Subjects on 1.2mg and experiencing mild nausea will continue on 1.2 mg for 2 more weeks. Subjects on Liraglutide 1.2mg daily without any gastro-intestinal side-effects will be asked to increase the dose to 1.8 mg daily. Study drug will be dispensed for additional 2 weeks.

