Study Visit week 4: Subjects will be asked to bring in their used study pens and the pen that they are using so that study nurse can log in the amount of drug used. If needed, the dose will be increased. The goal in the first 4 weeks is to increase patient's liraglutide dose to maximum tolerated dose. Maximum dose of liraglutide will be 1.8 mg daily. Subjects experiencing mild nausea with 0.6 mg or 1.2 mg will continue at that dose in the study. Those with severe nausea/vomiting with 1.8mg will decrease their dose to 1.2 mg and continue that dose throughout the study. Blood glucose concentrations will be reviewed. Insulin dose will be adjusted if needed. CGM will be discontinued. Study drug will be dispensed to last till the next visit.

Study visit week 8: Subjects will be asked to bring in their used study pens and the pen that they are using so that study nurse can log in the amount of drug used. Blood glucose concentrations will be reviewed. Insulin dose will be adjusted if needed. Study drug will be dispensed to last till the next visit.

Study Visit week 12: Subjects will be asked to bring in their used study pens and the pen that they are using so that study nurse can log in the amount of drug used. Blood glucose concentrations will be reviewed and vascular activity will be performed. Insulin dose will be adjusted if needed. Fasting blood, research labs, HbA1c, fructosamine, lipid panel, urine pregnancy test and 24 hr urine will be collected. FMD and 24hr blood pressure will be studied. Study drug will be dispensed for additional 4 weeks.

Study Visit week 16 and 20: Subjects will be asked to bring in their used study pens and the pen that they are using so that study nurse can log in the amount of drug used. Blood glucose concentrations will be reviewed. Insulin dose will be adjusted if needed. Study drug will be dispensed for additional 4 weeks.

Study visit week 24: CGM will be inserted. They will have their body composition measured by DEXA and MRI prior to next visit.

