Response: The following data will be collected during the conduct of the study based on the study design and protocol: HbA1c, fructosamine, average glucose, percent time spent in different glycemic thresholds, standard deviations which represent the variability in blood glucose, total insulin doses (basal dose, bolus dose and total daily dose), changes in carbohydrate intake and helpings; adverse events(including the most common side effects of nausea and vomiting which is often transient occurring at the time of initiation of liraglutide and at the time of escalation of the dose and the rare occurrence of pancreatitis, thyroid c-cell tumors and other patient reported adverse events which may occur anytime) and blood pressure. The principal investigator [name], PhD and co-investigators [name] and [name] will review the data every 3 months to assess the safety of the participants. Furthermore they will also assess other risks including the physical, psychological, social, legal and economic harm to these patients. The investigators listed above will carefully watch for any invasion of privacy and breach of confidentiality. The principal investigator will be sharing the results of safety analysis of the study with the sponsor (JDRF) and to the IRB. The study groups will remain blinded. If there are any safety concerns then co-investigator [name] who is not directly involved with the patients and or in insulin titrations of the study participants will unblind the study groups on the discretion of principal investigator and the team will assess potential harm to the patients and inform the IRB and sponsor of this potential harm. The corrective actions will then be taken and research subjects will be withdrawn from the study if risks outweigh the benefits. The IRB will be kept well-informed at all times. During each patient visit, evolution of glucose levels (CGM) will be conducted to reduce the risk of hypoglycemia or hyperglycemia. After recruitment and completion of half of the target number of patients i.e. 42 patients, interim analysis will be performed to determine an overwhelming harms or benefits with one treatment option compared to another.

 10.3 List any instruments or measurement tools used to collect data (e.g. questionnaire, interview guide, validated instrument, data collection form).

Include copies of these documents with your submission.

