17.0 Data Management and Analysis

17.1 Describe the data analysis plan, including any statistical procedures. This section applies to both quantitative and qualitative analysis.

Response: The focus of the proposed research is to evaluate the effect of liraglutide on mean HbA1c% over the period of 26 weeks of treatment. The similarities between the study groups, baseline values for subject's demographics and study endpoints will be compared using appropriate parametric tests. Transformations of the data in order to meet statistical assumptions may be considered. The **primary endpoint** of the study is to detect

a difference in HbA1c after 26 weeks of treatment with Liraglutide or placebo. The statistical analysis will be carried out using analysis of covariance (ANCOVA) and tested at the 0.05 level. Change in weight will be a covariate. The results will be computed as mean \pm SD. Analysis will be carried out on the basis of intention to treat (with last observation carried forward).

The secondary end points based on glycemic changes will include the difference from baseline in mean weekly glucose concentrations, standard deviations of the mean weekly glucose concentrations, HbA1c, fructosamine, the duration of time spent in hyperglycemia ($>150\text{mg/dl}$, $>200\text{mg/dl}$, $>250\text{mg/dl}$) and hypoglycemia ($<70\text{mg/dl}$, $<40\text{mg/dl}$), insulin dosage. A reduction in the AUC following the meal will constitute another secondary end point. Between groups comparisons of the magnitude of change from baseline will also be made for these glycemia related secondary endpoints using student's t-test. Comparisons for these and the primary endpoints will also be made using the paired t-test or Wilcoxon's test for paired data within each group.

The other secondary end-points of the study will be change from baseline after 26 weeks of treatment in the fasting and postprandial blood sugars, glucagon and C-peptide concentrations, indices of oxidative and inflammatory stress in MNC, plasma and adipose tissue; subcutaneous fat mass, hepatic fat content and visceral fat mass; features of metabolic syndrome; gastric emptying, blood pressure, vascular analysis, patient reported nausea, quality of life and depression scores. Between groups comparisons will be made using students t-test or ANCOVA (adjustment will be done for baseline differences). Within group comparisons for these endpoints will be made using paired t-test or Wilcoxon's test or ANCOVA.

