21.0 Risks to Subjects

21.1 List the reasonably foreseeable risks, discomforts, hazards, or inconveniences to the subjects related to their participation in the research. Consider physical, psychological, social, legal, and economic risks. Include a description of the probability, magnitude, duration, and reversibility of the risks.

NOTE: Breach of confidentiality is always a risk for identifiable subject data.

Response:

Subjects who experience severe nausea or vomiting after starting liraglutide will discontinue the study. Those with mild or moderate nausea will continue for at least one more week. If they continue to experience significant nausea (defined as interfering with normal activities), they will discontinue the study.

Subjects who develop pancreatitis will be withdrawn from the study.

Subjects who develop a new thyroid tumor during the study will be withdrawn. Patients will be informed that they should let study investigators know if they develop any swelling in the neck.

For the entire duration of the study, the patients will maintain a diary to record any hypoglycemia and other untoward side effects like nausea, changes in appetite and other experiences. Patients will be instructed to call the Diabetes Center to speak to a study investigator directly in case of any problem or untoward side effects. They will be specifically asked to call if they have hypoglycemia (blood sugar <70 mg/dl) or hyperglycemia (blood sugar >250 mg/dl) on more than one occasion. The target blood glucose during the study will be between 70-180mg/dl at all times, without increasing the incidence of blood glucose < 70 mg/dl.

The following Information from the boxed warning in the package insert regarding the risk of thyroid c-cell tumors will be discussed in details with all participating subjects:

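### Patient-reported nausea is analysed as a 26-week change from baseline, which mainly measures residual nausea in patients who tolerated treatment and would understate the difference between arms

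*Combined protocol and SAP*

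**What the plan says.** Section 17.1 opens its last group of endpoints with "The other secondary end-points of the study will be change from baseline after 26 weeks of treatment" and includes in that list "blood pressure, vascular analysis, patient reported nausea, quality of life and depression scores". Between-arm comparison is by Student's t-test or ANCOVA with adjustment for baseline. No nausea scale, recall period, or peak or cumulative summary is given. Nausea is not in the endpoint list of section 2.1, so 17.1 is the only place where it is defined as an endpoint.

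On the course of nausea and its handling:

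- Section 10.2 describes nausea and vomiting as "often transient occurring at the time of initiation of liraglutide and at the time of escalation of the dose".
- Section 10.1, week 4: "The goal in the first 4 weeks is to increase patient's liraglutide dose to maximum tolerated dose".
- Section 10.1, week 1: "Those with severe nausea/vomiting will be dropped from the study". At week 2, significant nausea leads to removal at 0.6 mg and to a lower dose at 1.2 mg. At week 4, severe nausea or vomiting at 1.8 mg leads to a lower dose. Mild nausea at 0.6 or 1.2 mg continues on that dose.
- Section 21.1: throughout the study "the patients will maintain a diary to record any hypoglycemia and other untoward side effects like nausea".
- Sections 19.2 and 19.5: nausea and vomiting are among the adverse events collected at visits and by telephone. Section 19.3 names hypoglycemia as the only safety endpoint. Section 19.8 lists the t-test, chi-square and Wilcoxon tests for safety data without naming a variable.

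**The concern.** A change score at week 26 compares two moments: before treatment and the last visit. By the protocol's own account, nausea is expected mostly between them. A patient who was nauseated in weeks 1 to 4 and recovered has the same week-26 change as a patient who never had nausea. Those with the worst nausea have by then left or moved to a lower dose.

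At stake is the one nausea comparison that the plan specifies. A small or null week-26 difference could be quoted as similar tolerability to placebo, even if nausea early in treatment had been clearly more common on liraglutide and had driven removals and dose reductions. The primary HbA1c comparison is not affected.

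**Working it through.** **Timing.** Escalation is meant to finish by about week 4 and the endpoint is read at week 26: 26 - 4 = 22 weeks later.

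**Who contributes a week-26 value.** Under section 10.1:

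| Visit | Nausea | Consequence | Observed at week 26? |
|---|---|---|---|
| Week 1 | severe nausea or vomiting | dropped | no |
| Week 2, 0.6 mg | significant | dropped | no |
| Week 2, 1.2 mg | significant | dose lowered | yes, on the lower dose |
| Week 4, 1.8 mg | severe nausea or vomiting | dose lowered | yes, on the lower dose |
| Week 4, 0.6 or 1.2 mg | mild | same dose | yes |

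Section 21.1 is worded differently: severe nausea, or significant nausea that persists, leads to discontinuation, with no dose-reduction step. The two sections must be reconciled. Under either, patients with the most nausea are absent from week 26 or observed on a changed dose.

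**Size.** The documents state no nausea rate, so there is no figure to reproduce. What follows is an illustration in which every rate is an assumption and nausea is scored as present or absent, because no scale is given.

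- p = proportion with nausea during escalation: 0.30, 0.40 or 0.50 on liraglutide, 0.10 on placebo.
- d = fraction of those patients dropped: 0.10 or 0.25.
- r = fraction of the remaining affected patients whose nausea has resolved by week 26: 0.50 to 1.00.
- d and r are the same in both arms; there is no nausea at baseline, no new nausea after escalation, and no dropout for other reasons.

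Formulas, per arm:

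- any nausea = p
- week 26, completers = p(1-d)(1-r) / (1-pd)
- week 26, last observation carried forward (LOCF) = p(1-d)(1-r) + pd

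One case, with p = 0.40 versus 0.10, d = 0.10, r = 0.75:

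- Any nausea: 0.40 - 0.10 = 0.30.
- Completers: liraglutide 0.40×0.90×0.25/0.96 = 0.094; placebo 0.10×0.90×0.25/0.99 = 0.023; difference 0.071.
- LOCF: liraglutide 0.090 + 0.040 = 0.130; placebo 0.0225 + 0.010 = 0.0325; difference 0.098.

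All cases, as differences in percentage points, with power in brackets (two proportions, 42 per arm, two-sided 0.05):

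| p on liraglutide | Any nausea | Week 26, completers | Week 26, LOCF |
|---|---|---|---|
| 0.30 | 20 (0.63) | 0 to 9.4 (0.03-0.31) | 2.0 to 12.5 (0.10-0.41) |
| 0.40 | 30 (0.90) | 0 to 14.2 (0.03-0.53) | 3.0 to 18.8 (0.14-0.66) |
| 0.50 | 40 (0.99) | 0 to 19.1 (0.03-0.72) | 4.0 to 25.0 (0.19-0.85) |

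The completer powers are flattering, because they use 42 per arm although some patients have left.

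Under LOCF the share of the escalation-phase difference that survives is d + (1-d)(1-r). It runs from 0.10 (d = 0.10, r = 1) to 0.25 + 0.75×0.50 = 0.625 (d = 0.25, r = 0.50). The week-26 difference is smaller in every case, and zero only in completers with full resolution.

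**The case against.** The strongest case against has four parts.

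*Nausea is captured elsewhere.* It is an adverse event collected at every visit and by telephone (19.2, 19.5), reviewed every 3 months (19.7), and 19.8 offers a chi-square test that would suit proportions by arm. This stands in part: the raw data would exist and could show early nausea. But section 19 defines no nausea variable, time window or population.

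*Some signal remains at week 26.* Section 10.2 says often transient, not always; mild nausea stays on dose; and a dose increase is still possible at week 4. This stands. A reader might infer that all affected patients are gone by week 4 and that the endpoint cannot show any nausea difference. The documents do not support that.

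*LOCF may help.* It is stated in the primary-endpoint paragraph of 17.1. If extended to nausea, patients dropped while nauseated would carry that value to week 26. This stands, but patients who recovered, including any who did so after a dose reduction, still enter with their week-26 value. The difference is recovered only in part.

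*The stakes are modest.* Nausea is in no aim, hypothesis or section 2.1 endpoint. This stands, and limits the point to a secondary tolerability measure.

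**Conclusion.** The point holds as one of attenuation. As defined in 17.1, the nausea endpoint mainly measures what remains at week 26 in patients who tolerated treatment, and would understate the between-arm difference. The direction rests on the protocol's own description of the time course and on its removal and dose-reduction rules. The amount is unknown. In the illustration, 0 to about 48% of the escalation-phase difference survives in completers (19.1/40 at most), and 10 to 62.5% under LOCF. These shares depend wholly on the assumed resolution and dropout.

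Two stronger readings are not supported. The first is that the week-26 difference will be about zero: that requires assuming near-complete resolution or equal week-26 rates in the arms, and the documents give neither. The second is that the trial will reach a wrong tolerability conclusion: adverse-event and withdrawal reporting under sections 19 and 20 could correct the picture. What is missing is a prespecified measure that does so.

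**What to change.** In section 17.1, remove patient-reported nausea from the 26-week change-from-baseline list and define it as follows:

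- **Measure:** the proportion of all randomised patients with any nausea from day 0 to week 26, taken from the existing diary and visit adverse-event records. Day 0 is included because a study injection is given then.
- **Events:** withdrawal or dose reduction because of nausea or vomiting counts as an event. The measure then does not depend on how sections 10.1 and 21.1 are reconciled.
- **Comparison:** between arms by chi-square or exact test, consistent with section 19.8.
- **Split:** also report weeks 0-4 and weeks 5-26. The second window should show how many patients were still under observation, since some will have left because of nausea.
- **Severity and duration:** report worst severity and nausea days only if the existing diary or adverse-event records capture them. Section 21.1 describes no severity scale or daily entry format, so these could otherwise need a new form.

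The cost is a change of wording and slightly more tabulation. No visit, procedure, dose rule or sample size changes.

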A recent trial of liraglutide, a glucagon like peptide (GLP)-1 analogue with a 24 hour duration of action, in 13 patients with type 1 diabetes led to a remarkable reduction in the excursions of blood glucose, both highs and lows, following meals and through the 24 hours within the first 2 days of treatment in all 13 subjects (7)(see preliminary data section). The mean glucose concentrations fell significantly from 136 to 111 mg/dl and the mean HbA1c fell significantly from 6.45 to 6.1% in 8 subjects who continued liraglutide for 24 weeks. The SD of glucose readings fell from 52 to 28. Remarkably, the requirement of insulin fell from 51 units to 28 units daily. The treatment also led to a reduction in appetite and to weight loss even during the short period of treatment for 9 weeks. The patients felt remarkably better and secure in terms of the 'predictability and stability' of glycemic and appetite control (7). The improvement in glycemia with the reduction in insulin requirements within days of starting treatment with liraglutide could be an evidence of insulin sensitization and /or endogenous insulinogenesis. Since C-peptide concentrations did not alter following the short term administration of liraglutide, it is likely that the suppression of glucagon may have contributed to this effect. It is also possible that the improvement in glucose homeostasis could partly have been due to a decrease in carbohydrate intake and reduced rate of gastric emptying, both of which are known actions of GLP-1 analogues (8, 9).

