17.2 If applicable, provide a power analysis.

NOTE: This may not apply to certain types of studies, including chart/records reviews, survey studies, or observational studies. This question is asked to elicit whether the investigator has an adequate sample size to achieve the study objectives and justify a conclusion.

Response: There are no prior randomized controlled trials that have examined the effect of Liraglutide on HbA1c in subjects with type 1 diabetes. In our observational study (preliminary data), we found a decrease in HbA1c of 0.35% after 6 months of liraglutide in patients with type 1 diabetes who had a mean HbA1c of $6.45\pm0.5\%$. In our proposed study, we will include patients with HbA1c up to 8.5%. Thus we expect a greater difference in HbA1c among the two groups at the end of the study. Conservatively estimating a difference in HbA1c of 0.35% between the two groups, a sample size of 32 patients per treatment group should provide 80% power to detect a significant difference ($\alpha = 0.05$), provided the standard deviation of the residuals is not greater than 0.5. Thus 64 subjects will be needed for the study. To account for a dropout rate of 30%, we will recruit 84 subjects into the study.

17.3 Describe any procedures that will be used for quality control of collected data.

Response: Three investigators and research nurse will double check the accuracy of collected data. All laboratory testing will be standardized using references and standards.

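### The stated 80% power is for 64 completers; the planned ITT-LOCF analysis of all 84 has about 69–73% if every leaver goes before week 12, and reaches 80% only if enough leave later with the effect kept

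*Combined protocol and SAP*

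**What the plan says.** Section 17.2 sets the effect by "Conservatively estimating a difference in HbA1c of 0.35% between the two groups". It states that "a sample size of 32 patients per treatment group should provide 80% power to detect a significant difference" at alpha 0.05, "provided the standard deviation of the residuals is not greater than 0.5". That makes 64 patients, and then: "To account for a dropout rate of 30%, we will recruit 84 subjects into the study". The 0.35 comes from the uncontrolled series in section 3.1, where "the mean HbA1c fell significantly from 6.45 to 6.1% in 8 subjects who continued liraglutide for 24 weeks".

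Section 17.1 gives the primary analysis as an ANCOVA "tested at the 0.05 level", with change in weight as covariate. On the analysis set and missing data it says: "Analysis will be carried out on the basis of intention to treat (with last observation carried forward". No completer analysis is described. Section 20.3 says that data gathered before withdrawal are used.

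Section 10.1 lists HbA1c at screening, week 12 and week 26 only. Its week 1 visit says: "Those with severe nausea/vomiting will be dropped from the study". Week 2 has a further nausea-related rule for leaving the study.

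**The concern.** The sample-size calculation and the primary analysis treat leavers differently. In 17.2 they disappear, and the 64 who remain all show the full 0.35. In 17.1 they stay, 42 per arm, with their last recorded HbA1c. The 0.35 was seen in patients who continued the drug, and nothing in the documents supports giving it in full to patients who stop. A leaver with no HbA1c after screening carries the screening value forward, so the analysed change is zero and the average difference shrinks.

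The 80% is therefore not the power of the analysis that will be reported. A non-significant ITT result read against 80% power for 0.35% could be taken as stronger evidence against an effect than it is.

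**Working it through.** **Inputs.** Difference on treatment 0.35, residual SD 0.5, alpha 0.05, 30% dropout, 84 randomised (all 17.2); 42 per arm (4.1). The plan does not state sidedness. Two-sided is assumed because it gives 33 per arm by the normal formula, close to the plan's 32; one-sided gives 26.

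**Formula.** Power of a two-sample t-test with n per arm: non-central t with 2n − 2 degrees of freedom and non-centrality δ / (s × √(2/n)).

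**The plan's figure.** n = 32, δ = 0.35, s = 0.5: non-centrality 0.35 / (0.5 × 0.25) = 2.80. Power is 80.0% by the normal approximation and 78.7% by the t distribution. The printed 80% is reproduced.

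**Completers if 30% really leave.** 42 × 0.70 = 29.4 per arm at 0.35 and 0.5: 75.1%. The 84 leaves 64 only if the loss is 1 − 64/84 = 23.8%.

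**ITT with LOCF.** Let e be the share of each arm that leaves before week 12 and so has zero change. Everyone else has SD 0.5 and, on liraglutide, the full 0.35. Then:

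- δ = 0.35 × (1 − e)
- variance on placebo = (1 − e) × 0.25
- variance on liraglutide = (1 − e) × 0.25 + e(1 − e) × 0.35²
- s = square root of the mean of the two variances

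For e = 0.30: δ = 0.245; variances 0.175 and 0.175 + 0.21 × 0.1225 = 0.2007; s = 0.433; non-centrality 0.245 / (0.433 × √(2/42)) = 2.59; power 72.6%.

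| Leavers | e | δ | s | Power, 42 per arm |
|---|---|---|---|---|
| 30%, all before week 12 | 0.300 | 0.245 | 0.433 | 72.6% |
| 30%, a quarter keep the full effect | 0.225 | 0.271 | 0.452 | 77.5% |
| 30%, 40% keep it | 0.180 | 0.287 | 0.463 | 80.2% |
| 30%, half keep it | 0.150 | 0.2975 | 0.469 | 81.9% |
| 30%, all keep it | 0 | 0.350 | 0.500 | 88.7% |
| 23.8%, all before week 12 | 0.238 | 0.267 | 0.449 | 76.7% |

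**With baseline HbA1c as a covariate.** The first row was also simulated as an ANCOVA. Baseline slope (0.6 to 1.0) and baseline SD (0.5 to 0.8) are assumptions, because the plan gives neither. Slopes of 0.8 to 1.0 give 71–73%. A slope of 0.6 gives about 69%, ranging from 67% to 71% over the baseline SDs. Hence about 69–73%.

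**Not only a matter of inflation.** Dividing instead, 64 / 0.70 gives 92, or 46 per arm. At e = 0.30 the ITT-LOCF power is then 76.5%, still below the 78.7% as sized.

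**The case against.** A reader might infer that the ITT analysis has only about 60% power. That figure comes from keeping s = 0.5 with δ = 0.245: non-centrality 0.245 / (0.5 × √(2/42)) = 2.25, power 60.2%. It requires leavers who show no effect yet contribute week-26 values with full variance. Under the plan's LOCF, a leaver without effect repeats the screening value and adds almost no residual variance. The 60% therefore belongs to an analysis the plan does not perform.

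Three further objections have weight.

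- **Timing is not documented.** The week 1 and week 2 rules point to some early leaving, but other patients with nausea stay in the study, and section 20.1 lists withdrawal reasons that can arise at any time. No rate or timing is given by arm. A late leaver carries a week-12 value that may hold much of the effect, and the shortfall disappears when about 40% of leavers keep all of it.
- **The plan calls 0.35 conservative** and expects more, though it gives no larger figure. With 30% early leavers, an on-treatment difference of 0.39 would give 80.8%. If 0.35 is read as the difference in the ITT analysis itself, 42 per arm gives 88.7%. The plan does not say which it means; its source, patients who continued the drug, favours the on-treatment reading.
- **The t-test is not exactly the planned model.** Section 17.1 adjusts for change in weight, which treatment itself may alter. None of the figures here allows for that.

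These objections limit the size of the shortfall. They do not remove the mismatch: 17.2 computes power for one set of patients, 17.1 analyses another, and the plan never says what leavers are expected to contribute.

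**Conclusion.** The point holds as a mismatch of modest and conditional size. At worst under the plan's own missing-data rule, with all 30% leaving before week 12, power is about 69–73%, some 6 to 10 points below the 78.7% as sized. With a 24% loss, or with a quarter of the 30% keeping the effect, the gap is 1 to 2 points. With about 40% or more keeping it, there is no shortfall.

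The documents do not support saying that the trial probably has 60–73% power, or that more patients are needed. The first drops the condition on timing and uses a variance that LOCF does not produce. The second credits nothing to late leavers or to the plan's view that 0.35 is conservative.

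Assumptions: two-sided alpha 0.05; equal dropout in both arms; ITT includes patients with no HbA1c after screening; no HbA1c is taken at an early-termination visit (section 20.2 lists none); leavers who keep the effect keep all of it; no adjustment for weight change.

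**What to change.** Reword the power statement in 17.2 to cover four things:

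- Label 0.35% with 80% power as a figure for 32 completers per arm, and add that it is about 75% if 30% are truly lost from 84.
- Give the power of the ITT-LOCF analysis with 42 per arm: about 69–73% if all 30% leave before week 12, rising to about 80% if close to half leave later with the effect retained.
- Say that these figures assume equal dropout by arm and no adjustment for weight change.
- Say whether 0.35 is meant as an on-treatment or an ITT difference, and that the plan regards it as conservative.

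Keep N at 84. The change needs no extra patients, visits or data. Its only cost is a slightly less favourable stated power.
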